8.7.7.1 Interim Analysis

The study will undertake a formal interim efficacy examination. An unblinded statistician that is not associated with a site, not part of the protocol team and not part of the operational support for this study will perform this analysis.

After half of the total sample size has completed 28 days of follow-up, primary analysis using the Fay-Shaw statistic (13) will be conducted. The study will be stopped for benefit if the one-sided p-value for benefit is less than .001. The study will be stopped for futility if the one-sided p-value for harm is less than .025.

9 STATISTICAL CONSIDERATIONS

This section briefly describes the statistical analyses to be used for the study. A Statistical Analysis Plan will provide further details.

9.1 General Considerations

This is a double-blind, randomized, placebo, controlled trial in patients with hospitalized influenza-like-illness to evaluate the efficacy of NTZ compared to placebo on the time to hospital discharge. The primary analysis will use the Shaw-Fay formulation of the 2 sample Mann-Whitney-Wilcoxon rank-sum statistic. The primary endpoint will be time to hospital discharge, censored at 28 days. Patients who withdraw consent will be counted as being censored at the time of withdrawal. Patients who die by Day 28 will receive the worst ranks, (i.e., worse than any patients who remain hospitalized). Furthermore, patients who die earlier will receive worse ranks than those who die later. Patients who withdraw consent prior to day 28 are thus censored for death and discharge at the time of withdrawal. Such censoring is addressed by the method of Shaw and Fay (2013). A permutation method will be used to determine statistical significance. The primary analysis will follow the intent-to-treat principle where all randomized patients will be used in the analysis. The primary analysis will use a two-sided alpha level of .05.

9.2 Sample Size and Power Calculations

Sample size calculations are based on the primary endpoint only (i.e. Duration of hospitalization). Secondary endpoints may or may not be adequately powered with the chosen sample size.

When there is no censoring or deaths, power for the two-sample Mann-Whitney-Wilcoxon rank-sum test can be approximated assuming that days of hospitalization follows a log normal distribution. The parameters used in the calculation were from the observed distribution of days to hospital discharge for hospitalized subjects who enrolled in the ILI002 observational study. We obtained data on patients who survived with hospitalization less than 28 days. The data were truncated at 28 days to avoid the influence of aberrant values on the estimates. This eliminated about 4% of the data. The mean and variance of the days in the hospital were 7.7 and 33.2. We assumed that the effect of treatment would be to reduce the number of days in the hospital by Delta but that there would be no effect of treatment on the variance of the number of days in the hospital. Thus for the treatment group the mean and variance are given by 7.7-Delta and 33.2, where Delta is varied. We next assume that the distribution of days to hospital discharge followed a log-normal distribution in each group, which is equivalent to assuming that the log(Days) follows a normal distribution, where Days is the number of days until hospital discharge. A log-normal distribution is specified by its moments $E\{\log(Days)\} = m$ and $\text{var}(\log(Days))=v$. These moments are related to the mean, $E(D)$, and variance, $V(D)$, of the number of days (D) in the hospital by the formulas.

$$m = \log\{E(D)\} - v/2$$

$$v = \log\{1 + V(D)/[E(D) \times E(D)]\}.$$

For simplicity, we determine the sample size for different assumptions of treatment effects of nitazoxanide, using a two sample t-test with unequal variances using Satterthwaite's method (Table 8). This method requires the mean and variance of log (Days) for the 2 groups, which are obtained by solving the above equations separately for the placebo and treatment groups. Calculations were performed using Nquery 7.0.

Table 9: The total sample size required to achieve different powers under different assumptions about the benefit of nitazoxanide (Delta) using a two-sided .05 level test

Moments for the log days in hospital						
	Placebo Group		Treatment Group			
Delta ^a	m ₀₀	Sqrt(v ₀)	m ₀	Sqrt(v ₀)	Power	N ^b
1.50 Days	1.83	.66	1.52	.78	80%	174
1.50 Days			1.52	.78	90%	232
1.25 Days	1.83	.66	1.58	.76	80%	258
1.25 Days			1.58	.76	90%	344
1.00 Day	1.83	.66	1.64	.74	80%	430
1.00 Day			1.64	.74	90%	576

^a Delta is the assumed reduction in the mean number of days in the hospital under treatment compared to placebo.

^b N is the total sample size.

We see that with about 258 patients total the study is 80% powered to detect a 1.25 day improvement in the time to hospital discharge. This difference is similar to our assumptions. To allow for up to 10% dropouts we will recruit 290 patients. If the difference was 1.5 days, the study would have 90% power to detect the difference in the treatment arms.

While a 1.25 day improvement is clinically meaningful and easily interpretable for a population with a mean hospital stay of 7.7 days, it is also a reasonable estimate of the effect of NTZ we might see. The NTZ IB describes a Phase 2b-3 study in adults and adolescents with acute uncomplicated ILI. In all subjects, the mean time to resolution of symptoms was 95 hours in the NTZ group compared to 108 hours in the placebo group, thus there is about a 12% reduction in the time to resolution (12% = (108 hr - 95 hr)/108 hr x 100%). Our hoped for treatment effect of a 1.25 day reduction in hospital duration is a 16% reduction in the time to hospital discharge (16% = (1 day/7.7 day x 100%)).

Kaplan Meier curves of time to hospitalization discharge over 28 days will be used to compare the 2 groups. In these curves, deaths will be counted as being in the hospital at day 28. The between group difference in median time to discharge will be used to estimate the treatment effect and will be reported along with a 95% two-sided confidence interval.

Important additional analyses will be to repeat the primary analysis for those who are influenza positive. Other subgroups include age (<12 years of age, \geq 12 years of age) and pathogen type.

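### Section 9.2 states 80% power for 1.25 days without its condition (no deaths, no stays to Day 28), although the primary rank test puts exactly those patients at the worst ranks

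*Protocol*

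**What the plan says.** Protocol section 9.2 opens with a condition: "When there is no censoring or deaths, power for the two-sample Mann-Whitney-Wilcoxon rank-sum test can be approximated" by assuming log-normal hospital days. The planning data come from the ILI002 cohort under a matching restriction: "We obtained data on patients who survived with hospitalization less than 28 days". On the effect of truncating at 28 days it says "This eliminated about 4% of the data". The remaining patients had mean 7.7 days and variance 33.2. Sample sizes then come from a Satterthwaite t-test on log days (Table 9, cited in the text as Table 8).

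The conclusion, given after the table, is that "with about 258 patients total the study is 80% powered to detect a 1.25 day improvement". It continues: "To allow for up to 10% dropouts we will recruit 290 patients" and "If the difference was 1.5 days, the study would have 90% power to detect the difference". The opening condition is not repeated.

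The primary test is defined elsewhere. Protocol section 9.1 censors time to discharge at 28 days and says "Patients who die by Day 28 will receive the worst ranks", below anyone still in hospital. SAP Appendix 1 gives the same order: deaths worst, then patients not discharged by Day 28, then late and early discharges. Neither document gives a death rate, a rate of stays to Day 28, or power under this ranking.

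**The concern.** The 80% is the stated justification for N, and a null result will be read against it. It was derived in a population from which the patients with the worst outcomes had been removed, but it is stated for a trial whose primary test keeps them.

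A few percent of patients at the extreme ranks can matter. If they are equally frequent in both arms, they carry large ranks and no treatment signal, so they add noise and dilute the difference. If treatment also makes them rarer, they add signal and power recovers. Section 9.2 does not say which it assumes, so a reader cannot recover the power of the primary test from either document.

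**Working it through.** **1. The plan's own figure reproduces.** The Table 9 moments for 1.25 days are: placebo mean 1.83, SD 0.66; nitazoxanide mean 1.58, SD 0.76. With 129 per arm:

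- SE = √[(0.66² + 0.76²)/129] = √(1.0132/129) = 0.0886
- noncentrality = (1.83 − 1.58)/0.0886 = 2.82
- power from the noncentral t with Satterthwaite df (about 251) = 80.2%

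For 1.5 days (1.52, 0.78) with 116 per arm, the SE is 0.0949, the noncentrality 0.31/0.0949 = 3.27, and power 90.2% at 232. All six sample sizes in the table reproduce from its printed moments.

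Putting 7.7 and 33.2 directly into the section's formulas gives v = ln(1 + 33.2/7.7²) = 0.4447, SD 0.667 and m = 1.819. For mean 6.45 it gives 1.571 and 0.766. Power at 258 is then 79.0%, a small rounding difference. Both sets of moments are used below.

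**2. Which patients enter which calculation.**

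| Patients | Power calculation (9.2) | Primary test (9.1, SAP Appendix 1) |
|---|---|---|
| Discharged alive before Day 28 | included | included |
| In hospital at Day 28 | removed | next-worst ranks |
| Died by Day 28 | removed | worst ranks |
| Withdrew | allowed for: 258/0.9 = 287, rounded up to 290 | kept, censored |

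The gap is the second and third rows.

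**3. Power of the rank test with those rows restored.** This is a simulation of the two-sided 0.05 rank-sum test with tie-corrected permutation variance, 20,000 trials per cell for most rows (Monte Carlo standard error 0.2-0.35 point). Day-28 stays are tied at 28; deaths, where included, rank worse, with earlier deaths worst. Each range spans Table 9 or formula moments, with the log-normal either capped or truncated at 28 days. The 4% is the protocol's figure; equal rates in both arms and the other rates are assumptions.

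| Worst-rank patients (placebo / nitazoxanide) | Delta, days | N = 258 | N = 290, all followed |
|---|---|---|---|
| none added | 1.25 | 77-80% | 82-84% |
| 2% / 2% | 1.25 | about 75% | 78-81% |
| 4% / 4%, all Day-28 stays | 1.25 | 70-73% | 75-78% |
| 4% / 4%, half deaths | 1.25 | 70-73% | 75-78% |
| 4% / 3% | 1.25 | 75-78% | 80-83% |
| 4% / 2% | 1.25 | 81-83% | 85-87% |
| 8% / 8% (4% stays plus 4% deaths) | 1.25 | 63-65% | 68-71% |
| 4% / 4% | 1.5 | 85-88% | 89-91% |

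Restoring 4% equally costs about 6-8 points. How the 4% divides between deaths and long stays hardly matters; its total and any treatment effect on it do. With 4% in both arms, about 320 analysable patients would be needed for 80%.

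**4. Minor slip.** The section justifies its 16% reduction as "16% = (1 day/7.7 day x 100". But 1/7.7 = 13.0%; the intended figure is 1.25/7.7 = 16.2%. The stated 16% and N do not change.

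**The case against.** The strongest reply is that section 9.2 discloses its simplification openly, a page before the conclusion, and that the conclusion only reads off the table. That stands as to candour: this is not an arithmetic error, and a reader who infers that 258 was miscalculated would be wrong. It does not supply the missing quantity, which is power for the ranking actually used.

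Three further points stand and limit the charge.

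- **Withdrawals.** A reader might add them to the omitted groups. The documents do not support that: the rise from 258 to 290 treats each withdrawal as a total loss, while the primary test keeps it as censored. In simulation, 10% withdrawing at random times over 28 days left power at 290 at 75-78%, the same as full follow-up. That run used an approximation to the Shaw-Fay ranks, because the documents do not print the formula.
- **The 1.5-day statement.** It is approximately kept: about 89-91% at 290 with 4% in both arms.
- **Equal rates are not the only reasonable case.** The protocol hypothesises better outcomes generally, including ICU and oxygen needs, so treatment may also reduce long stays. The 4% comes from an observational cohort. This trial excludes suspected bacterial illness, patients unable to take enteral medication, and more than 60 hours of prior hospitalisation, so its own rate may differ.

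The rise to 290 does not answer the main point. It is assigned to dropouts, and even with nobody lost, 4% in both arms gives 75-78%.

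**Conclusion.** The 80% for 1.25 days holds for patients discharged alive before Day 28. It is not established for the primary test. With the protocol's own 4% restored equally in both arms, power is roughly 70-73% at 258 and 75-78% at 290. At 290 it is about 80% if the rate is nearer 2% in both arms or if treatment lowers the 4% to about 3%.

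It would be tempting to conclude that the trial is underpowered and N must rise. The documents do not support that: the answer depends on death and long-stay rates, and on a treatment effect on them, that are not stated. Section 9.2 also leaves unclear whether the 4% includes deaths.

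The figures depend on the model. Capping leaves a further 1.1-1.2% beyond Day 28 on top of the 4%; truncating cuts the variance to about 21-23, against 33.2. A log-normal fitted so that its truncated moments match the protocol's gives about 60% at 258 with 4% in both arms, partly because its spread is wider. The direction under equal rates is firm; the exact level is not. Type I error and the planned confidence interval are unaffected.

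**What to change.** Keep N = 290, the endpoint, the test and alpha. In section 9.2:

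1. Attach the condition to the 80% sentence, so that it says the figure is for a log-scale t-test among patients discharged alive before Day 28, with no censoring or deaths.
2. Add the team's own simulated power for the primary rank test with 290 randomised, using the R code promised in SAP Appendix 1. Cover a stated range of death and Day-28-stay rates that includes 4% in both arms, with and without a treatment effect on them. The figures above are a guide, not text to adopt.
3. State whether the eliminated 4% includes deaths, and use the ILI002 death rate if it is available.
4. Correct the fraction behind the 16% to 1.25/7.7.

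The cost is one short simulation and a few sentences. The price is a less favourable and wider stated power, and an explicit assumption about deaths and long stays.

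### Table 9's sample sizes come from log-scale moments rounded to two decimals and from a t-test; with the stated inputs and the planned rank test, 258 fully informative patients give about 77% power for 1.25 days, not 80%

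*Protocol*

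**What the plan says.** Protocol section 9.2 takes its planning data from an observational cohort: "The mean and variance of the days in the hospital were 7.7 and 33.2". These are survivors with stays under 28 days. Under treatment, "for the treatment group the mean and variance are given by 7.7-Delta and 33.2, where Delta is varied". Days are assumed log-normal in each arm, and two formulas convert the mean and variance of days into the mean and variance of log days. The sample size is then found "using a two sample t-test with unequal variances using Satterthwaite's method", which the protocol describes as a simplification.

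The Table 9 row that drives the design reads "1.25 Days 1.83 .66 1.58 .76 80% 258". The text concludes that "with about 258 patients total the study is 80% powered to detect a 1.25 day improvement", allows for up to 10% dropouts, and recruits 290. It adds that a 1.5-day difference would be detected with 90% power.

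The test that will be run is different. Section 9.1 says: "The primary analysis will use the Shaw-Fay formulation of the 2 sample Mann-Whitney-Wilcoxon rank-sum statistic". It also says: "The primary analysis will use a two-sided alpha level of .05".

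**The concern.** A reader who puts 7.7 and 33.2 into the protocol's formulas does not arrive at 258. The test that was sized is also not the primary test, and the rank test is slightly less efficient than a t-test on log-normal data. At 1.25 days both gaps push the required number up. Section 9.2 is the only justification given for the enrolment target, so the stated 80% should follow from the stated inputs and the planned test. The question is separate from deaths and losses to follow-up, because it arises even when there are none.

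**Working it through.** **Inputs (protocol sections 9.1 and 9.2).** Placebo mean 7.7 and variance 33.2; treated mean 7.7 − Delta and variance 33.2; 1:1 allocation; two-sided alpha .05.

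**1. Reproducing the plan's figures.** Table 9's printed moments were entered in a noncentral-t power calculation with Satterthwaite degrees of freedom. For n per arm the noncentrality is (m₀ − m₁) / √((s₀² + s₁²)/n). At Delta 1.25 and n = 129 this is 0.25 / √((0.66² + 0.76²)/129) = 2.821, and power is 80.2%. All six sample sizes come out exactly: 174, 232, 258, 344, 430 and 576.

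**2. Moments from the stated inputs.** The formulas are v = log{1 + V/E²} and m = log E − v/2.

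- Placebo: v = log(1 + 33.2/7.7²) = 0.4447, so √v = 0.667 and m = 1.819.
- Treated, Delta 1.25 (mean 6.45): v = log(1 + 33.2/6.45²) = 0.5867, so √v = 0.766 and m = 1.571.

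The table prints 1.83 / .66 and 1.58 / .76. The noncentrality at n = 129 becomes 0.248 / √((0.667² + 0.766²)/129) = 2.775. T-test power at 258 is then 79.0%, and 80% needs 266.

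**3. Could rounding of 7.7 and 33.2 explain the difference?** For the moments, yes. A mean near 7.745 with a variance near 33.16 prints as 7.7 and 33.2, and yields every Table 9 moment to two decimals. For the sample sizes, no. The ranges below cover all means from 7.65 to 7.75 and variances from 33.15 to 33.25, with unrounded moments and the same t-test:

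| Delta | Printed N (80% / 90%) | From 7.7 and 33.2 | Range over inputs that print as 7.7 and 33.2 |
|---|---|---|---|
| 1.50 | 174 / 232 | 182 / 244 | 180–184 / 242–246 |
| 1.25 | 258 / 344 | 266 / 354 | 264–268 / 352–358 |
| 1.00 | 430 / 576 | 422 / 562 | 418–424 / 558–568 |

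No printed N lies inside its range. At 1.5 and 1.25 days the printed figure is too small; at 1.0 day it is conservative. The natural explanation is that the moments were rounded to two decimals before the sample size was computed.

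**4. The planned test.** Log-normal data were simulated from the stated inputs and analysed with the Mann-Whitney-Wilcoxon test (100,000 to 200,000 replicates per setting; no deaths, no censoring). At Delta 1.25:

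| Fully informative patients | Power |
|---|---|
| 258 | about 77% |
| 260 | about 77.5% |
| 278 | 80.0% |
| 280 | 80.3% |
| 290 | 81.5–82% |

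With Table 9's own moments, the rank test gives about 78.3% at 258. Of the 3-point gap at 258, about 1 point is therefore moment rounding and about 2 points are the change of test.

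**5. Dropout.** 258/0.9 = 286.7, that is 287, and the plan recruits 290. If 10% of 290 contributed nothing, 290 × 0.9 = 261 would remain, with power of about 77 to 78%.

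**6. The 1.5-day statement.** From the stated inputs, the rank test has about 90% power at 258 and about 87% at Table 9's 232.

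**The case against.** The best defence has four parts.

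- **The t-test is disclosed.** Section 9.2 presents it as a simplification, and that choice accounts for about 2 of the 3 points. This stands as an explanation. But the protocol does not say what the simplification costs, and it attaches the 80% to the study, whose test is the rank test.
- **The protocol's own calculation is barely affected.** At 258 the t-test still has 79.0% power, and the text says about 258. This stands: rounding alone would hardly merit a comment.
- **The figure of 77% is not the power at the recruited number.** Recruitment is 290, and the Shaw-Fay method keeps withdrawals as censored observations instead of dropping them. Treating 10% as contributing nothing is a worst case, and with all 290 informative the rank test exceeds 80%. This stands, and it is why the target need not change.
- **The recalculation is itself idealised.** It assumes exactly log-normal stays, no deaths and no censoring. This also stands, and the restated power should carry those conditions.

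Two stronger readings are tempting. A reader might infer that Table 9's moments are wrong. The documents do not support that, because a mean that prints as 7.7 can produce all of them; only the sample sizes fail to follow. A reader might also infer that both gaps are unfavourable throughout. At 1.0 day the rounding works the other way and nearly offsets the change of test: rank-test power is about 79.4% at 430 and 89.4% at 576.

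**Conclusion.** The point holds as a correction to the stated power. Table 9's sample sizes do not follow from the stated mean, variance and formulas, and they are for a test that will not be used. At 1.25 days the shortfall at 258 is about 3 percentage points (77% against 80%), and 80% needs about 278 to 280 informative patients. These figures rest on log-normal stays with mean 7.7 and variance 33.2, unchanged variance under treatment, and no deaths or censoring. The documents give no death rate for the planning data, so the effect of deaths was not estimated.

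It would go too far to conclude that the trial is underpowered or must enrol more patients. Power lies between about 77% and 82%, according to how much information dropouts retain, and it exceeds 80% if all 290 are informative. Nor does the text's 90% power at 1.5 days fail: it holds at 258, and only the tabulated 232 falls short.

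**What to change.** Recompute Table 9 from unrounded moments for the Mann-Whitney-Wilcoxon test. In section 9.2, restate the power for a 1.25-day reduction as about 77% with 258 fully informative patients and about 82% with all 290, and say that this assumes no deaths or censoring. Keep the target of 290.

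The cost is a few revised figures and a slightly less favourable power statement. No patients are added, and the endpoint, test and alpha level are unchanged.

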9.3 Subject Populations

Intention to Treat (ITT) Population: The ITT population will consist of all participants who are randomized and received at least 1 dose of the study drug. For interim reviews, this will be limited to data entered into the electronic database up to the cut-off date.

9.4 Statistical Analysis

The Statistical Analysis Plan will provide the procedure for accounting for missing, unused, and spurious data.

10 DATA MANAGEMENT AND MONITORING

10.1 Study Monitoring

The trial will be conducted in compliance with this protocol, International Conference on Harmonization (ICH) Guidelines for Good Clinical Practice (GCP), the Food and Drug Administration's (FDA) Code of Federal Regulations (CFR) and any applicable regulatory requirement(s). This study monitoring will be conducted according to the "NIAID Intramural Clinical Monitoring Guidelines." Monitors under contract to the NIAID will visit the clinical research site to monitor all aspects of the study in accordance with the appropriate regulations. The objectives of a monitoring visit will be:

1. To verify the prompt reporting of all data points, including reporting SAEs, and also to check the availability of signed informed consent.
2. To compare individual subjects records and the source documents (supporting data, laboratory specimen records and medical records to include physician progress notes, nurse' notes, subjects' hospital charts).
3. To ensure compliance with the protocol, and accuracy and completeness of records.

The monitors also will inspect the clinical site regulatory files to ensure that regulatory requirements (Mexican and US) are being followed. During the monitoring visits, the Investigator (and/or designee) and other study personnel will be available to discuss the study progress and monitoring visit. The Sponsor will retain original copies of the Form FDA 1572 and copies of other study documents as deemed necessary.

The Investigator (and/or designee) will make study documents (e.g., consent forms and eCRFs) and pertinent hospital or clinical records readily available for inspection by the local IRB/IEC, the local and national regulatory authorities, the US FDA, the site monitors, and the NIAID staff for confirmation of the study data.

